16.5 Appendix 5: Patient Past History and Disease Characteristics

AML diagnosis: diagnosis of AML will be reported as defined by the 2016 World Health Organization (WHO) AML classification (Arber et al 2016).

Table 16-7 2016 WHO AML classification

1	AML with recurrent genetic abnormalities	 AML with t(8;21)(q22;q22), RUNX1-RUNX1T1. AML with inv(16)(p13.1;q22) or t(16;16)(p13.1;q22), CBFB-MYH11. Acute promyelocytic leukemia (APL) with PML-RARA. AML with t(9;11)(p21.3;q23.3), MLLT3-KMT2A. AML with t(6;9)(p23;q34.1), DEK-NUP214. AML with inv(3)(q21.3;q26.2) or t(3;3)(q21.3;q26.2), GATA2, MECOM.
		 AML (megakaryoblastic) with t(1;22)(p13.3;q13.3), RBM15-MKL1. AML with BCR-ABL1 (provisional entity). AML with mutated NPM1.
		AML with biallelic mutations of CEBPA. AML with mutated BLINY1 (provisional antity)
2	AML with myelodysplasia- related features	AML with mutated RUNX1 (provisional entity).
3	Therapy-related myeloid neoplasms	
4	AML, Not Otherwise Specified (NOS)	 AML with minimal differentiation (FAB classification M0). AML without maturation (FAB classification M1). AML with maturation (FAB classification M2). Acute myelomonocytic leukemia (FAB classification M4). Acute monoblastic/monocytic leukemia (FAB classification M5a and M5b). Pure erythroid leukemia (FAB classification M6a and M6b). Acute megakaryoblastic leukemia (FAB classification M7). Acute basophilic leukemia. Acute panmyelosis with myelofibrosis.
5	Myeloid sarcoma	
6	Myeloid proliferations related to Down syndrome:	 Transient abnormal myelopoiesis (TAM). Myeloid leukemia associated with Down syndrome.
7	Acute Leukemias of Ambiguous Lineage	 Acute undifferentiated leukemia. Mixed phenotype acute leukemia (MPAL) with t(9;22)(q34.1;q11.2); BCR-ABL1. MPAL with t(v;11q23.3); KMT2A rearranged. MPAL, B/myeloid, NOS.

		MDAL T/myoloid NOS
	•	MPAL, T/myeloid, NOS.

Cytogenetics and risk stratification: cytogenetic risk category will be reported according to the 2017 European LeukemiaNet (ELN) recommendations (Döhner et al 2017).

Table 16-8 2017 ELN risk stratification by genetics

Risk category*	Genetic abnormality
Favorable	t(8;21)(q22;q22.1); RUNX1-RUNX1T1
	inv(16)(p13.1q22) or t(16;16)(p13.1;q22); CBFB-MYH11
	Mutated NPM1 without FLT3-ITD or with FLT3-ITD ^{low} †
	Biallelic mutated CEBPA
Intermediate	Mutated NPM1 and FLT3 -ITD ^{high} †
	Wild-type NPM1 without FLT3 -ITD or with FLT3 -ITD ^{low} † (without adverse-risk genetic lesions)
	t(9;11)(p21.3;q23.3); MLLT3-KMT2A ‡
	Cytogenetic abnormalities not classified as favorable or adverse
Adverse	t(6;9)(p23;q34.1); DEK-NUP214
	t(v;11q23.3); KMT2A rearranged
	t(9;22)(q34.1;q11.2); BCR-ABL1
	inv(3)(q21.3q26.2) or t(3;3)(q21.3;q26.2); GATA2,MECOM(EVI1) -5 or del(5q); -7; -17/abn(17p)
	Complex karyotype,§ monosomal karyotype
	Wild-type NPM1 and FLT3 -ITD ^{high} †
	Mutated RUNX1{
	Mutated ASXL1{
	Mutated TP53#

Frequencies, response rates, and outcome measures should be reported by risk category, and, if sufficient numbers are available, by specific genetic lesions indicated.

†Low, low allelic ratio (,0.5); high, high allelic ratio (\$0.5); semiquantitative assessment of *FLT3*-ITD allelic ratio (using DNA fragment analysis) is determined as ratio of the area under the curve "*FLT3*-ITD" divided by area under the curve "*FLT3*-wild type"; recent studies indicate that AML with *NPM1* mutation and *FLT3*-ITD low allelic ratio may also have a more favorable prognosis and participants should not routinely be assigned to allogeneic HCT.

‡The presence of t(9;11)(p21.3;q23.3) takes precedence over rare, concurrent adverse-risk gene mutations.

§Three or more unrelated chromosome abnormalities in the absence of 1 of the WHO-designated recurring translocations or inversions, that is, t(8;21), inv(16) or t(16;16), t(9;11), t(v;11)(v;q23.3), t(6;9), inv(3) or t(3;3); AML with BCR-ABL1.

||Defined by the presence of 1 single monosomy (excluding loss of X or Y) in association with at least 1 additional monosomy or structural chromosome abnormality (excluding core-binding factor AML).

{ These markers should not be used as an adverse prognostic marker if they co-occur with favorable-risk AML subtypes.

#TP53 mutations are significantly associated with AML with complex and monosomal karyotype.

Molecular markers and risk stratification:

^{*}Prognostic impact of a marker is treatment-dependent and may change with new therapies.

In addition to basic cytogenetic analysis, molecular markers that can help refining prognostics groups, particularly in participants with a normal karyotype, include: NPM1, FLT3 (FLT3-ITD and FLT3-TKD), CEBPA, isocitrate dehydrogenase 1 and 2 (IDH1/2), DNA methyltransferase 3A (DNMT3A), c-KIT, MLL, TP53, RUNX1, and ASXL1 gene mutations (National Comprehensive Cancer 2020).

16.6 Appendix 6: Statistical details on the Bayesian Logistic Regression Model (BLRM)

Statistical Models

The safety run-in part of this study to confirm that the sabatolimab is safe will be guided by a Bayesian analysis of dose limiting toxicity (DLT) data. The statistical model will be a Bayesian Logistic Regression Model (BLRM) consisting of a single agent dose-DLT component.

Let π (d) be the risk of DLT for sabatolimab given as a single agent Q4W at dose d. The single agent dose-DLT model is as follow:

 $logit(\pi(d)) = log(\alpha) + \beta log(d/d^*)$

where d*= 800 mg Q4W (reference dose of sabatolimab) is used to scale the doses of sabatolimab. Hence, α (>0) is the single-agent odd of a DLT at 800 mg Q4W; β (>0) is the increase in the log-odds of a DLT by a unit increase in log-dose.

Taking into account the intrinsic risk of GvHD (which is part of the DLT definition) in the posttransplant setting, we selected a weakly informative prior with means corresponding to a risk of DLT at the reference dose of 15%, and a doubling in dose leading to a doubling in the odds of the risk of a DLT.

No meta-analytic-predictive (MAP) approach was used to derive the prior distribution as historical data are not available in this post-transplant setting.

The prior distribution is specified in Table 16-9.

Table 16-9 Prior distribution

Parameter	Prior distribution		
μ1	N(mean = logit(0.15), sd = 2)		
μ2	N(mean = 0, sd=1)		

The recommended dose for expansion will be the highest dose between 400 mg and 800 mg Q4W for which the probability of excessive toxicity (i.e. DLT rate $\geq 50\%$) is less than 0.25.

The summary of prior distribution of DLT rates is specified in Table 16-10.

Summary of prior distribution of DLT rates **Table 16-10**

Dose of sabatoli mab	Prior probabilities that P(DLT) is in the interval: [0, 0.50) [0.50,1]		Mean	SD	Quantiles	;			
					2.5%	50%	97.5%		
400 mg Q4W	0.897	0.103	0.163	0.220	0.000	0.061	0.813		
800 mg Q4W	0.806	0.194	0.257	0.264	0.003	0.151	0.900		

Hypothetical on-study scenarios

To illustrate the performance of the BLRM used to guide the tolerability assessment in the safety run-in part for sabatolimab in monotherapy, hypothetical data scenarios are displayed in Table 16-11. Decision will be based on additional safety, PK or PD information.

Table 16-11 Probability of unacceptable toxicity for different hypothetical scenarios

Number of participants with at least one DLT (including GvHD) among evaluable participants		Probability to observe a DLT rate with three different definition of over-toxicity (>40%, >45% or >50%)						
		DLT rate >40%		DLT rate >45%		DLT rate >50%		
1st cohort 400 mg	2nd cohort 800 mg	Next dose*	P(excessive toxicity)	Next dose*	P(excessive toxicity)	Next dose*	P(excessive toxicity)	
1/6		800	0.219	800	0.166	800	0.125	
2/6		400	0.211	400	0.145	400	0.094	
3/6		stop		Stop		stop		
2/8		400	0.094	400	0.055	800	0.216	
3/8		stop		400	0.199	400	0.129	
0/6	2/9	800	0.038	800	0.016	800	0.007	
0/6	3/9	800	0.136	800	0.076	800	0.040	
0/6	4/9	400	0.012	800	0.214	800	0.134	
0/6	5/9	400	0.025	400	0.012	400	0.005	
1/6	3/9	800	0.212	800	0.125	800	0.068	
1/6	4/9	400	0.068	400	0.033	800	0.184	
1/6	5/9	400	0.130	400	0.072	400	0.036	
2/8	3/9	400	0.052	800	0.179	800	0.097	
2/8	4/9	400	0.106	400	0.053	800	0.224	

^{*} Next dose is the dose recommended by the BLRM for the next cohort or the expansion part of the study that satisfies the definition of an acceptable level of toxicity (probability of excessive toxicity (i.e. DLT rate ≥ 40, 45 or 50%) is less than 0.25.

Operating characteristics

The following exact operating characteristics were performed for different true values of DLT rate observed in the safety run-in part (participants treated with sabatolimab in monotherapy at 400 or 800 mg Q4W). Based on simulations with a 50% threshold to qualify for an excessive toxicity: when the true DLT rate observed in participants treated with sabatolimab 400 mg and 800 mg is equal to 40% and 50% respectively, the probability to stop the trial is 0.38 and the probability to start the expansion part of the trial with sabatolimab at 400 mg and 800 mg is 0.50 and 0.13 respectively (Table 16-12).

Table 16-12 Operating characteristics for different true values of DLT rate

True DLT rates	Probability to declare an excessive toxicity for three
	different thresholds to qualify for an excessive toxicity

1st cohort	2nd cohort	DLT rate >40%			DLT rate >45%			DLT rate >50%		
400 mg	800 mg	400 mg	800 mg	both doses	400 mg	800 mg	both doses	400 mg	800 mg	both doses
15%	20%	0.248	0.683	0.049	0.244	0.709	0.047	0.170	0.806	0.024
20%	30%	0.413	0.427	0.160	0.386	0.502	0.112	0.306	0.615	0.079
30%	40%	0.472	0.163	0.365	0.504	0.213	0.283	0.477	0.318	0.205
40%	50%	0.372	0.053	0.575	0.448	0.079	0.473	0.496	0.127	0.377

Operating characteristics are performed with R3.6.1 with 1000 simulations and by considering a sample size of 6 to 8 participants for the first cohort and a sample size of 9 to 12 participants for the second cohort.

Date	Time point	Reason for update	Outcome for update	Section and title impacted (Current)	
10- June- 2021	FPFV	Creation of version 1.0	N/A - First version (based on protocol from 30-Sep-2020)	N/A	
03-Jul- 2024	Before primay CSR DBL	Creation of version 2.0	Amendment 2 (based on protocol from 24- March-2022) and MBG453 program termination	 Sections updated based on the protocol amendment 2 dated from 24 March 2022: Section 1.2.1: primary safety and efficacy estimand definitions Section 2.1: clarification of general definition Sections updated due to MBG453 program termination and thus, simplification of the analyses: Section 1: general statement added. Addition of a column in the 	
				 objectives tables to summarize the analyses performed for this final analysis. Section 2.1: general statement added. Section 2.3.1: simplification of protocol deviations summaries and deletion of pre-screened and screened failures analyses Section 2.4.1: cycle delays analysis deleted Section 2.4.2: Clarifications. Donor Lymphocyte Infusions will be only listed. Section 2.5 and 2.6: general statement added. Following endpoints were flagged as not assessable: Primary safety analysis in adolescents p-value deleted for the primary efficacy analysis in adults GvHD-free/relapse-free survival Section 2.7: AEs, SAEs, COVID-19 related events, GvHD, severe immune-related adverse events not attributed to GvHD, AESI and vital signs analyses simplified. Figures and corresponding tables for hematology parameters deleted Section 2.8: PK analyses simplified Section 2.6: Listings of all responses assessments added. 	

Date	Time point	Reason for update	Outcome for update	Section and title impacted (Current)
				Section 5: updated date of last exposure to study treatment and duration of exposure to study treatment derivation
				Typos corrected
				Clerical updates
				Updating of list of Abbreviatons

List of abbreviations

AE	Adverse event
AESI	Adverse events of special interest
aGvHD	Acute Graft-versus-Host disease
ALT	Alanine aminotransferase
AML	Acute myeloid leukemia
AST	Aspartate aminotransferase
ATC	Anatomical therapeutic classification
BLQ	Below the limit of quantitation
BMI	Body mass index
BP	Blood pressure
BSA	Body surface area
cGvHD	Chronic Graft-versus-Host disease
CI	Confidence interval
CR	Complete remission
CRi	Complete remission with incomplete hematologic recovery
CSR	Clinical study report
СТС	Common toxicity criteria
CTCAE	Common terminology criteria for adverse events
CV	Coefficient of variation
DDS	Dose-determining set
DLI	Donor lymphocyte infusion
DLT	Dose limiting toxicity
DMS	Document Management System
eCRF	Electronic case report form
eCRS	Electronic case retrieval strategy
ECG	Electrocardiogram
ECOG	Eastern Cooperative Oncology Group
EFS	Event free survival
ELN	European Leukemia Net
EORTC QLQ-C30	European Organisation for Research and Treatment of Cancer - Quality of Life Questionnaire
EOT	End of treatment
EQ-5D-5L	EuroQol Group - standardized measure of health status questionnaire
FAS	Full analysis set
GRFS	GvHD-free/relapse-free survival
GvHD	Graft versus host disease
HSCT	Hematopoietic stem cell transplantation
IST	Immunosuppressive treatment
LAIP	Leukemia associated immunophenotype
MedDRA	Medical Dictionary for Regulatory Activities
MLFS	Morphologic leukemia free state
MRD	Measurable residual disease

OS	Overall survival
PD	Progressive disease
PFS	Progression-free survival
PGI	Patient global impression
PK	Pharmacokinetics
PR	Partial remission
PT	Preferred term
QoL	Quality of life
Q4W	Every 4 weeks
RAP	Report and analysis process
RBC	Red blood cells
RDE	Recommended dose for expansion
RFS	Relapse free survival
SAE	Serious adverse event
SAP	Statistical analysis plan
SD	Stable disease
SMQ	Standardized MedDRA Query
SOC	System organ class
SoC	Standard of Care
TFLs	Tables, figures, listings
WHO	World Health Organization

1 Introduction

This statistical analysis plan (SAP) describes the planned analyses for the final Clinical Study Report (CSR) of the sabatolimab Study CMBG453F12201, A phase Ib/II, open label study of sabatolimab as a treatment for patients with acute myeloid leukemia and presence of measurable residual disease after allogeneic stem cell transplantation (aHSCT).

As specified in Section 12.7 of the study protocol, interim analyses are planned for the monitoring of safety data, and will be conducted after each dose level cohort of the safety runin part to determine the recommended dose for expansion (RDE) (primary safety objective). This SAP will serve as the basis for those analyses as well; however, a separate selection of tables, figures and listings (TFL) will be done.

The content of this SAP is based on the CMBG453F12201 protocol amendment 2 (24-Mar-2022). All decisions regarding the analysis, as defined in the SAP document, have been made prior to database lock.

Due to the study recruitment halt and the termination of the MBG453 program for non-safetyrelated reasons, this study will be terminated early. Thus, not all protocol planned derivations and analyses will be performed. Although described in this document, please refer to table of endpoints for the selected planned analyses of this final CSR. Any secondary endpoint analyses not conducted due to limited number of patients available, will be documented as such in the final CSR and indicated as zero patients with an explanation for mandatory results posting, if required.

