GRFS is defined as the time from start of treatment to the date of first documented occurrence or worsening of treatment emergent grade III or IV aGvHD or moderate to severe cGvHD requiring initiation of systemic treatment, hematologic relapse, or death due to any cause, whichever occurs first. GRFS will be censored if no GRFS event is observed before the first to occur between: (i) the analysis cut-off date, and (ii) the date when a new anti-neoplastic therapy or a donor leucocytes infusion (DLI) is started. The censoring date will be the date of the last adequate response assessment prior to cut-off/start of new anti-neoplastic therapy or DLI.

GRFS will be analyzed in the FAS population and the GRFS distribution will be estimated using the Kaplan-Meier method. Kaplan-Meier curves, medians and 95% confidence intervals of the medians will be presented for each dose cohort.

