Study treatment consists of cycles of sabatolimab (400 mg or 800 mg) administered intravenous on Day 1 of each 28-day cycle for the monotherapy cohorts (Cohorts 1, 2, 4 and 5). Study treatment consists of cycles of sabatolimab (400 mg or 800 mg) administered on Day 5 of each 28-day cycle in combination with azacitidine administered intravenous or subcutaneous at 50 mg/m² daily during the first 5 days of each cycle (Cohort 3). Crossover between the different sabatolimab doses (400 mg and 800 mg Q4W) is not permitted at any time during the study. Study treatment may continue for up to a maximum of 24 cycles or until the participant experiences a documented hematologic relapse from CR/CRi (as defined by ELN 2017 Döhner et al 2017) or unacceptable toxicity, whichever is earlier.

Interim analyses are planned for the monitoring of safety data, and will be conducted after each dose level cohort of the safety run-in part to determine the RDE. The first safety review meeting to assess whether sabatolimab 400 mg Q4W is not meeting overdose criteria (i.e. an excessive incidence of Dose Limiting Toxicities (DLT)) will take place after at least 6 evaluable participants treated with sabatolimab 400 mg Q4W have completed 2 cycles of treatment (Cohort 1). If no safety concerned are observed at this dose level, a second safety review meeting to assess whether sabatolimab 800 mg Q4W is not meeting overdose criteria will take place after at least 9 evaluable participants treated with sabatolimab 800 mg Q4W is not meeting overdose criteria will take place after at least 9 evaluable participants treated with sabatolimab 800 mg Q4W have completed 2 cycles of treatment (Cohort 2). Details on the definition of dose limiting toxicities (DLT) are presented in study protocol Table 6-2.

The efficacy of sabatolimab when given as a single agent or in combination with azacitidine will be assessed after all adults from Cohorts 3 and 4 have completed 6 cycles of treatment (primary efficacy objective). The end of study is defined as all participants having completed the safety and post-treatment follow up (if applicable), or having died, been lost to follow-up or having withdrawn consent to further participation in the study.

Due to the study recruitment halt and the termination of the sabatolimab program for non-safetyrelated reasons, the study will be terminated early. Based on the limited numbers of participants, the final CSR will be written with a limited number of analyses.

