For adolescents only: To determine whether sabatolimab as monotherapy at the recommended dose level for adults leads to an unacceptable level of toxicity when administered to adolescent participants with AML who are in complete remission but are MRD+ post- aHSCT.	 Incidence of treatment-emergent dose limiting toxicities (DLTs), including aGvHD and cGvHD during the first 2 cycles of study treatment. 	• No
Secondary objective(s)	Endpoint(s) for secondary objective(s)	
To assess the incidence of grade III or IV aGvHD and moderate to severe cGvHD.	 Incidence of treatment emergent grade III or grade IV aGvHD. Incidence of treatment emergent moderate to severe cGvHD. 	• No

Objective(s)	Endpoint(s)	Final CSR
To characterize the pharmacokinetics (PK) of sabatolimab.	• Summary of serum concentrations (pre-dose samples) and pharmacokinetic parameters (the minimum observed plasma or serum drug concentration: Cmin) for sabatolimab.	• Yes
 To assess GvHD-free/relapse- free survival (GRFS). 	Time from start of treatment to the date of first documented occurrence or worsening of treatment emergent grade III or IV aGvHD or moderate to severe cGvHD requiring initiation of systemic treatment, hematologic relapse, or death due to any cause, whichever occurs first.	• No
To assess Relapse-Free Survival (RFS).	• Time from start of treatment to the date of first documented hematologic relapse or death due to any cause, whichever occurs first.	• Yes
• To determine the safety and tolerability of sabatolimab in monotherapy and in combination with azacitidine.	 Incidence and severity of AEs and SAEs, changes in laboratory values and vital signs. 	• Yes
To assess severe immune- related adverse events not attributed to GvHD.	 Incidence of treatment-emergent ≥ grade 3 immune-related adverse events not attributed to GvHD. 	• Yes
 To assess the proportion of participants with centrally confirmed MRD+ at screening who become MRD- during the first 6 cycles of study treatment. 	• Proportion of participants with centrally confirmed MRD+ status at baseline converting to MRD-within the first 6 cycles of study treatment.	• Yes

Objective(s)	Endpoint(s)	Final CSR

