2.6.1 Secondary endpoints

Relapse-Free Survival (RFS)

RFS is defined as the time from start of treatment to the date of first documented hematologic relapse or death due to any cause, whichever occurs first. RFS will be censored if no RFS event is observed before the first to occur between: (i) the analysis cut-off date, (ii) the date when a new anti-neoplastic therapy or a donor lymphocyte infusion (DLI) is started, and (iii) lost to follow-up or withdrawal of consent. The censoring date will be the date of the last adequate response assessment prior to cut-off/start of new anti-neoplastic therapy or DLI. The handling of intercurrent events will be the same as the primary estimand.

RFS will be analyzed in the FAS population and the RFS distribution will be estimated using the Kaplan-Meier method. Kaplan-Meier curves, medians and 95% confidence intervals of the medians will be presented for each dose cohort.

The following events could occur during the study and may affect the interpretation of the results:

- Start of donor lymphocyte infusions (DLI) or a new anti-neoplastic therapy: For a participant without an event before the time he/she receives any DLI or further anti-cancer therapy, RFS would be censored at the date of the last adequate assessment prior to start of DLI or further anti-neoplastic therapy.
- Stopping study treatment (including due to toxicities): All events will be taken into account when they occur, regardless of any study treatment interruption or permanent discontinuation.
- Discontinuation from study due to lost to follow-up or withdrawal of consent: For a participant without an event prior to discontinuation due to lost to follow-up or withdrawal of consent, RFS will be censored at the last adequate assessment date.

In case of two or more missing assessments prior to documented relapse or death, RFS will be censored at the last adequate response assessment prior to the documentation of relapse or death. The rule to determine whether there are two missing assessments is described in Section 2.6.3.

The RFS censoring reason will be summarized as:

- 1. Ongoing without event
- 2. New anti-neoplastic therapy
- 3. Donor lymphocyte infusions
- 4. Withdrew consent
- 5. Lost to follow-up
- 6. Event documented after two or more missing response assessments

GvHD-free/relapse-free survival (GRFS) - Not assessable

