GRFS is defined as the time from start of treatment to the date of first documented occurrence or worsening of treatment emergent grade III or IV aGvHD or moderate to severe cGvHD requiring initiation of systemic treatment, hematologic relapse, or death due to any cause, whichever occurs first. GRFS will be censored if no GRFS event is observed before the first to occur between: (i) the analysis cut-off date, (ii) the date when a new anti-neoplastic therapy, or a donor lymphocyte infusion (DLI) is started, and (iii) lost to follow-up or withdrawal of consent.

Novartis	Confidential	Page 25 of 35
SAP – Amendment 1		CMBG453F12201

The censoring date will be the date of the last adequate response assessment prior to cut-off/start of new anti-neoplastic therapy or DLI.

GRFS will be analyzed in the FAS population and the GRFS distribution will be estimated using the Kaplan-Meier method. Kaplan-Meier curves, medians and 95% confidence intervals of the medians will be presented for each dose cohort.

The following events could occur during the study and may affect the interpretation of the results:

- Start of donor lymphocyte infusions (DLI) or a new anti-neoplastic therapy: For participant without an event before the time he/she receives any DLI or further anti-cancer therapy, GRFS will be censored at the date of the last adequate assessment prior to start of DLI or further anti-neoplastic therapy.
- Stopping study treatment (including due to toxicities): All events will be taken into account when they occur, regardless of any study treatment interruption or permanent discontinuation.
- Discontinuation from the study due to lost to follow-up or withdrawal of consent: For participants without an event prior to discontinuation due to lost to follow-up or withdrawal of consent, GRFS will be censored at the last adequate assessment date.

In case of two or more missing assessments prior to documented relapse or death or treatment emergent grade III or IV aGvHD, or moderate to severe cGvHD requiring initiation of systemic treatment, GRFS will be censored at the last adequate response assessment prior to the documentation of the event. The rule to determine whether there are two missing assessments is described in Section 2.6.3.

The GRFS censoring reason will be summarized as:

- 1. Ongoing without event
- 2. New anti-neoplastic therapy
- 3. Donor lymphocyte infusions
- 4. Withdrew consent
- 5. Lost to follow-up

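### SAP v2 drops GRFS as not assessable but keeps RFS in the same participants, and its stated reasons do not separate the two

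*SAP*

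**What the plan says.** Protocol Table 2-1 lists RFS and GRFS as separate secondary endpoints. Protocol 12.5.1 commits to the second: "GRFS will be analyzed in the FAS population and the GRFS distribution will be estimated using the Kaplan-Meier method", with curves, medians and confidence intervals by dose cohort.

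SAP v2 is dated 3 July 2024, after the recruitment hold of December 2023, and reduces the report. Its reasons are general:

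- Section 1: "Any secondary endpoint analyses not conducted due to limited number of patients available, will be documented as such in the final CSR". Such endpoints may be posted as zero patients with an explanation.
- Section 1.1: "Based on the limited numbers of participants, the final CSR will be written with a limited number of analyses".
- Version history, under changes attributed to programme termination: "Following endpoints were flagged as not assessable". GRFS is one of those named.

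Table 1-1 marks RFS 'Yes' and GRFS 'No' for the final report. In 2.6.1 the heading is "GvHD-free/relapse-free survival (GRFS) - Not assessable", yet the full definition, censoring rules and analysis still follow it. For the endpoint that is kept, the same section says "RFS will be analyzed in the FAS population and the RFS distribution will be estimated using the Kaplan-Meier method".

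SAP section 4, on changes to the protocol's analyses, reads 'Not applicable'.

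**The concern.** Sabatolimab is meant to strengthen the graft-versus-leukemia effect. Protocol 1.1 and 1.2 name worsening GvHD as the principal safety concern of doing so. GRFS is the planned endpoint that counts GvHD against relapse prevention in one time-to-event measure, and RFS ignores GvHD by construction. If only RFS is estimated, the report shows how long participants stayed alive and relapse-free, but not how long they did so without serious GvHD.

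Dropping one of the pair needs a reason that applies to that one and not the other. The other endpoint flagged in the version history, adolescent DLT incidence, has such a reason: SAP 1.2.1 and 2.5 say that only one adolescent was enrolled. GRFS has none.

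**Working it through.** The documents state no event count, power or precision for RFS or GRFS, so there is no figure to reproduce. The check sets the two definitions side by side and reasons from the event sets.

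**Comparison (SAP Table 1-1 and 2.6.1)**

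| Attribute | RFS | GRFS |
|---|---|---|
| Final report | Yes | No |
| Set | FAS | FAS |
| Time zero | Start of treatment | Start of treatment |
| Method | Kaplan-Meier by dose cohort | Kaplan-Meier by dose cohort |
| Censored for | Cut-off, new therapy or DLI, loss or withdrawal | Same |
| Events | Relapse, death | Grade III-IV aGvHD, or "moderate to severe cGvHD requiring initiation of systemic treatment, hematologic relapse, or death due to any cause, whichever occurs first" |

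**Event ordering.** Let R be the time to relapse or death, G the time to qualifying GvHD and C the censoring time. RFS has an event if R ≤ C. GRFS has an event if min(R, G) ≤ C. Since min(R, G) ≤ R, every participant with an RFS event also has a GRFS event, at the same time or earlier.

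**Exception.** Under the two-missed-assessments rule, an event too long after the last adequate response assessment is censored back to that assessment. SAP 2.6.3 sets the limit at 10 weeks up to Cycle 4, 28 weeks from Cycle 4 to Cycle 13, and 56 weeks after that. A GvHD event beyond the limit would be censored for GRFS. If response assessments then resumed and a relapse followed, the same participant would have an RFS event. This is possible but should be rare.

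**Expected events (illustration).** Assumptions: exponential times; median time to relapse or death 7 months, borrowing the relapse median in protocol 1.1, which was measured from transplant in people who relapsed; 12 months of follow-up; independent GvHD with 12-month risk p.

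- Free of an RFS event at 12 months: 2^(−12/7) = 0.305
- Expected RFS events: n × (1 − 0.305) = 0.695n
- Expected GRFS events: n × (1 − 0.305 × (1 − p))

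| n | RFS | GRFS, p = 0% | p = 15% | p = 30% | p = 50% |
|---|---|---|---|---|---|
| 5 | 3.5 | 3.5 | 3.7 | 3.9 | 4.2 |
| 10 | 7.0 | 7.0 | 7.4 | 7.9 | 8.5 |
| 20 | 13.9 | 13.9 | 14.8 | 15.7 | 17.0 |

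At none of these sizes does GRFS have fewer events, so small numbers alone cannot rule out GRFS while allowing RFS.

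**Difference in the estimates (illustration).** With an assumed RFS of 40% and qualifying GvHD in 15% to 30% of relapse-free participants, GRFS is 0.40 × 0.85 = 0.34 to 0.40 × 0.70 = 0.28. The gap is 6 to 12 percentage points, or about one participant in a cohort of 10 (0.6 to 1.2).

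**The case against.** A reader might infer three stronger things. The documents do not support them.

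**That GvHD goes unreported.** It does not. Acute and chronic GvHD are part of the retained DLT endpoint (SAP Table 1-1), are included in the adverse event tables (SAP 2.7.1), and are listed with maximum stage by organ (SAP 2.7.1.1). These are partial substitutes. DLTs cover two cycles in the adult safety run-in. The adverse event tables use CTCAE grade, which protocol 6.5.3 and 10.1.1 set aside for GvHD. The incidence endpoint for severe GvHD is also marked 'No', so the summaries planned in protocol 12.5.2 become listings.

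**That results drove the choice.** The trial is open-label and the SAP was revised after accrual stopped, so influence is possible. But the halt is described as unrelated to safety, SAP section 1 says that decisions preceded database lock, and the omission is disclosed in three places. Nothing shows that outcomes guided it.

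**That GRFS cannot be less assessable than RFS.** Event count is not the only requirement. Protocol Tables 8-1 and 8-2 schedule response and cGvHD assessments in post-treatment follow-up but none for aGvHD, and 8.4.4.1 leaves later aGvHD assessment to clinical indication. Protocol 8.4.4.2 has the overall cGvHD grade reported at diagnosis, whereas GRFS also counts worsening, and exclusion criteria 5 and 6 allow entry with milder GvHD. These are real ascertainment limits. The SAP does not cite them, and they call for a caveat more than for omission.

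It is also fair that the SAP never ties the GRFS flag to small numbers by name, that no secondary efficacy endpoint is formally tested (SAP 2.6.2), and that trial success does not depend on RFS or GRFS.

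**Conclusion.** The asymmetry is real and unexplained. One of two parallel secondary endpoints is kept and the other dropped, for general reasons that apply equally to both. GRFS will almost always have at least as many events as RFS; the only exception found is the two-missed-assessments rule. Of this pair, only the endpoint that ignores GvHD will be estimated, and no retained analysis combines GvHD with relapse and death over time.

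The size cannot be derived from the documents. The gap of 6 to 12 points rests wholly on assumed rates and is not an estimate. Because the report is abbreviated and these endpoints are descriptive, this is a worthwhile and cheap improvement to reporting, not a flaw that alters the trial's conclusions.

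**What to change.** 1. In SAP Table 1-1 change GRFS to 'Yes', and delete 'Not assessable' from its heading in 2.6.1.
2. Report GRFS beside RFS by dose cohort, with counts of first-event type: relapse, death, aGvHD, cGvHD. If curves are uninformative at these numbers, give event and censoring counts for both endpoints instead.
3. Extend the missing-assessment rule in 2.6.3 to GRFS. The GRFS text refers to it, but it is written for RFS only.
4. State beside the GRFS results that aGvHD has no scheduled assessment in post-treatment follow-up.
5. Record in SAP section 4 any protocol endpoint still dropped. If GRFS stays out, give a reason specific to it.

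Label: cheap improvement. The cost is SAP wording plus a derivation beyond the RFS programme: GvHD onset, worsening from baseline, and start of systemic treatment. Protocol 8.4.4 places GvHD grading, treatment of cGvHD and management of aGvHD on the CRFs, although worsening of cGvHD may be incompletely captured. Intervals will be wide, as they will be for RFS.
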